11.0 CRITERIA FOR RESPONSE OR PROGRESSION

11.1 Efficacy Assessments

Progression-free survival (PFS) and objective response rate (ORR), each based on RECIST 1.1 criteria, are two of the primary efficacy assessments of this study.

Evaluation of response will follow the Response Evaluation Criteria in Solid Tumors (RECIST). All tumor measurements must be recorded in centimeters.

- Target Lesions:
All measurable lesions up to a maximum of 2 lesions per organ and 5 lesions in total, representative of all involved organs, should be identified as target lesions and recorded and measured at baseline. Target lesions should be selected on the basis of their size (those with the longest diameter) and their suitability for accurate repeated measurements (either by imaging techniques or clinically). A sum of the longest diameter for all target lesions will be calculated and reported as the baseline sum longest diameter. The baseline sum of longest diameters will be used as the reference by which the objective tumor response is characterized.
- Non-target Lesions:
All other lesions (or sites of disease) up to 2 lesions per site and 5 lesions in total should be identified as non-target lesions and should also be recorded at baseline. Measurements of these lesions are not required, but the presence or absence of each should be noted throughout follow-up.

Proprietary of MD Anderson Cancer Center

11.2 Evaluation of Target Lesions:

- Complete Response (CR):
The disappearance of all target lesions.
- Partial Response (PR):
At least a 30% decrease in the sum of the longest diameter of target lesions, taking as reference the baseline sum longest diameter.
- Progressive Disease:
At least a 20% increase in the sum of the longest diameter of target lesions, taking as reference the smallest sum longest diameter recorded since the treatment started or the appearance of one or more new lesions.
- Stable Disease:
Insufficient shrinkage to qualify for partial response, or insufficient increase to qualify for progressive disease, taking as reference the smallest sum longest diameter since the treatment started.

11.3 Evaluation of Non-target Lesions:

- Complete Response:
The disappearance of all non-target lesions.
- Incomplete Response/Stable Disease:
The persistence of one or more non-target lesion(s)
- Progressive Disease:
The appearance of one or more new lesions and/or unequivocal progression of existing non-target lesions.

11.4 Evaluation of Best Overall Response:

The best overall response is the best response recorded from the start of treatment until disease progression/recurrence (taking as reference for progressive disease the smallest measurements recorded since the treatment started).

Evaluation of Best Overall Response (RECIST)

Target Lesions	Non-target lesions	New lesions	Overall response
CR	CR	No	CR
CR	Incomplete response/SD	No	PR
PR	Non-PD	No	PR
SD	Non-PD	No	SD
PD	Any	Yes or no	PD
Any	PD	Yes or no	PD
Any	Any	Yes	PD

CR= complete response; PR= partial response; SD= stable disease; and PD= progressive disease

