4.0 ELIGIBILITY CRITERIA

4.1 Signed written informed consent

1. Patients must give written informed consent prior to initiation of therapy, in keeping with the policies of the institution. Patients with a history of major psychiatric illness must be judged able to fully understand the investigational nature of the study and the risks associated with the therapy.

4.2 Inclusion criteria:

1. Patients with histologically or cytologically confirmed metastatic/advanced clear cell RCC, or RCC with a clear cell component, who have received 1 or 2 prior anti-angiogenic therapy regimens (+/- cytokine therapy with interleukin-2 or interferon-alfa) in the advanced or metastatic setting. Examples of anti-angiogenic agents include, but are not limited to, sorafenib, sunitinib, pazopanib, axitinib, and bevacizumab.
2. There must be evidence of progression on or after last treatment regimen received and within 6 months of enrollment.
3. Patients must have at least one measurable site of disease, defined as a lesion that can be accurately measured in at least one dimension (longest diameter to be recorded) and measures \geq 15 mm with conventional techniques or \geq 10 mm with more sensitive techniques such as MRI or spiral CT scan. If the patient has had previous radiation to the marker lesion(s), there must be evidence of progression since the radiation.
4. Karnofsky performance status \geq 70

5. Age \geq 18 years
6. Patients must have adequate organ and marrow function prior to study entry as defined below:
 - Hemoglobin^a \geq 9 g/dl (treatment allowed)
 - absolute neutrophil count \geq 1,500/ μ L
 - platelets \geq 100,000/ μ L
 - total bilirubin \leq 1.5 mg/dl
 - AST(SGOT) or ALT (SGPT) \leq 2.5 X institutional uln, except in known hepatic metastasis, wherein may be \leq 5 x ULN
 - Serum Creatinine \leq 1.5 x ULN (as long as patient does not require dialysis)

^a May receive transfusion

^bIf creatinine is not $<1.5 \times$ ULN, then calculate by Cockcroft-Gault methods or local institutional standard and CrCl must be \geq 40 mL/kg/1.73 m²

7. INR and PTT \leq 1.5 x ULN prior to study entry. Therapeutic anticoagulation with warfarin is allowed if target INR \leq 3 on a stable dose of warfarin or on a stable dose of low molecular weight (LMW) heparin for $>$ 2 weeks (14 days) at the time of enrollment.

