8.3 Continued Treatment beyond Progression of Disease

Accumulating evidence indicates a minority of patients treated with immunotherapy may derive clinical benefit from continued treatment despite initial evidence of progressive disease.⁶⁷ For this reason, patients will be permitted to continue study therapy beyond initial investigator-assessed RECIST 1.1-defined progression as long as they meet the 2 criteria listed below.

- Investigator-assessed clinical benefit, and
- Subject is tolerating study drug

The assessment of clinical benefit should take into account whether the subject is clinically deteriorating and unlikely to receive further benefit from continued treatment.

All decisions to continue treatment beyond initial progression must be discussed with the MDACC IND Office and documented in the study records.

Patients should discontinue study therapy upon evidence of further progression, defined as an additional 10% or greater increase in tumor burden from time of initial progression (including all target lesions and new measurable lesions).

New lesions are considered measurable at the time of initial progression if the longest diameter is at least 10 mm (except for pathological lymph nodes, which must have a short axis of at least 15 mm). Any new lesion considered non-measurable at the time of initial progression may become measurable and therefore included in the tumor burden measurement if the longest diameter increases to at least 10 mm (except for pathological lymph nodes, which must have an increase in short axis to at least 15 mm).

For statistical analyses that include the investigator-assessed progression date, patients who continue treatment beyond initial investigator-assessed RECIST 1.1-defined progression will be considered to have investigator-assessed progressive disease at the time of the initial progression event.

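### Section 11.1 caps the non-target lesions that are recorded, so clear progression of baseline disease beyond the caps can be scored as SD or PR instead of PD

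*Combined protocol and SAP*

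**What the plan says.** Section 11.1 selects targets as "All measurable lesions up to a maximum of 2 lesions per organ and 5 lesions in total". The next bullet sets similar limits for everything else: "All other lesions (or sites of disease) up to 2 lesions per site and 5 lesions in total should be identified as non-target lesions". These lesions are followed only qualitatively: "Measurements of these lesions are not required, but the presence or absence of each should be noted throughout follow-up".

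Section 11.3 defines non-target CR as "The disappearance of all non-target lesions" and non-target PD as "The appearance of one or more new lesions and/or unequivocal progression of existing non-target lesions". The overall-response table in Section 11.4 has three inputs: target lesions, non-target lesions and new lesions.

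The same classification feeds several endpoints. Sections 5.3 and 14.1 count CR, PR or SD within 6 weeks as Efficacy for Lo-EffTox, with the week-6 scan read by RECIST 1.1. Section 11.1 ties ORR and PFS to RECIST 1.1, and Section 11.6 repeats this for PFS.

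**The concern.** A cap on targets is workable because non-target follow-up picks up the rest of the disease. Here the non-target list is capped too, although its lesions need no measurement. A lesion present at baseline but outside both lists is not target, not non-target, and not new. Nothing in the plan says that it must still be followed or counted.

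Read literally, growth in that disease cannot produce PD. Because SD is a success in the dose-finding outcome, a missed PD enters Lo-EffTox as a success and not as a failure. The same miss delays or removes a PFS event and, when the targets have shrunk enough, can leave a patient counted as a responder.

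**Working it through.** No sample-size or power formula applies. The check has three steps: count what the caps allow, trace an unrecorded lesion through the table, and scale one re-scored patient.

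**1. Capacity of the caps (Section 11.1).** Per patient, at most 5 + 5 = 10 lesions are recorded. Per organ, at most 2 + 2 = 4. Examples with all lesions measurable:

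| Lesions at baseline | Target | Non-target | Unrecorded |
|---|---|---|---|
| 4 in one organ | 2 | 2 | 0 |
| 5 in one organ | 2 | 2 | 1 |
| 10 in one organ | 2 | 2 | 6 |
| 4 in each of three organs | 5 | 5 | 2 |
| 10, 4 and 2 in three organs | 5 | 5 | 6 |

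Fewer lesions can suffice when some are not measurable. One measurable and three non-measurable lesions in one organ give 1 target + 2 non-target = 3 recorded, with 1 of 4 left out.

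**2. Tracing the unrecorded lesions through Sections 11.2 to 11.4.** The third column shows the result if the same lesions counted as non-target.

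| Situation, no truly new lesion | Table as written | If counted as non-target | What changes |
|---|---|---|---|
| A. Targets SD, recorded non-targets not PD, unrecorded lesions clearly progress | SD | PD | Efficacy, PFS |
| B. As A, but targets PR | PR | PD | Efficacy, PFS, and ORR if there was no earlier response |
| C. Targets and recorded non-targets gone, unrecorded lesions persist without progressing | CR | PR | CR label only |
| D. Targets SD or PR, nothing progresses, but an unrecorded baseline lesion is later taken for a new one | PD | SD or PR | Efficacy, PFS, possibly ORR, in the opposite direction |

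In C, CR and PR are both Efficacy successes, both count in ORR, and neither is a PFS event. Paths A and B are the ones on which the point rests.

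**3. Scale.** Section 3.4 reports 42 patients, with 15 started at 80 mg and 24 at 120 mg. Its overall figures reproduce: ORR 15/42 = 35.7%, disease control 37/42 = 88.1%, CR 1/42 = 2.4%.

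- One patient re-scored at 80 mg: 1/15 = 6.7 points.
- One patient re-scored at 120 mg: 1/24 = 4.2 points.
- One patient in the overall disease control rate: 1/42 = 2.4 points.
- If 1 to 5 disease-control patients were really PD (an assumed range): 36/42 = 85.7% down to 32/42 = 76.2%.
- If one reported PD were a path D error: 38/42 = 90.5%.

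These figures show the weight of a patient. They are not estimates of how many were misclassified. Section 3.4 gives no week-6 Efficacy counts by dose, and no section gives lesion counts.

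**The case against.** Several counter-arguments deserve weight.

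- **Grouping may already be allowed.** The bullet mentions sites of disease as well as lesions, so one entry might cover an organ. But it then limits lesions per site and asks for the status of each. At best the text is ambiguous.
- **RECIST 1.1 is named and governs.** Section 11 can be read as a summary of it. But Section 11.1 prints its own instruction on what to record, and staff will follow that.
- **Other safeguards exist.** A new lesion is PD wherever it appears. Sections 8.0 and 12.0 let the investigator take rapidly progressing patients off treatment, Section 15.0 makes the principal investigator final arbiter of response, and the irRC table in Section 11.5 requires all lesions to disappear for CR. These lower the practical risk. None puts an unrecorded lesion into the RECIST classification on which week-6 response, ORR and PFS depend.
- **Misclassification needs discordance.** Targets are chosen by size and must represent all involved organs, so unrecorded lesions will often behave like recorded ones. This stands: having an unrecorded lesion is not the same as being misclassified.
- **The change comes late.** Section 3.4 already reports 42 patients and favours a starting dose, and the extension phase has no formal RECIST measurements. This stands too. New wording cannot alter dose assignments already made.

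A reader might also infer a fault in node measurement. Section 11.2 defines progression as "At least a 20% increase in the sum of the longest diameter of target lesions" with no separate rule for nodes, while Section 8.3 treats new lesions as measurable from 10 mm "except for pathological lymph nodes, which must have a short axis of at least 15 mm". It is tempting to conclude that a small node could be the sole target and turn to PD on trivial growth. The documents do not support that as a contradiction. Section 8.3 concerns new lesions counted in tumour burden after initial progression, not baseline targets. Section 4.2 requires accurate measurability, and Section 11.1 requires suitability for repeated measurement. The documents also state no minimum absolute growth to hold the plan to. At most, the node wording in Sections 4.2, 8.3 and 11.1 should be reconciled.

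**Conclusion.** The gap is real and follows from the plan's own wording. Baseline disease beyond the caps cannot trigger PD, so paths A and B can turn true progression into an Efficacy success and a missed PFS event. One such patient is worth 6.7 points of the efficacy rate at 80 mg or 4.2 points at 120 mg. This assumes that the rule was applied literally and that recorded and unrecorded lesions behaved differently.

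Three stronger readings are not supported:

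- A reader might infer that the cap inflates efficacy overall. Path D works the other way, although the baseline imaging required by Section 9.1 makes that error less likely. Without lesion counts neither direction can be weighted.
- A reader might infer that the reported results or the preference for 120 mg are wrong, given the close desirability scores in Section 3.4 (0.787 at 80 mg, 0.755 at 120 mg). Nothing in the documents shows that any patient was misclassified.
- A reader might infer that false CRs matter for the endpoints. Mere persistence of unrecorded lesions changes only the CR label, and one CR in 42 is reported.

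The wording should be corrected because doing so is nearly free, not because harm has been shown.

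**What to change.** In Section 11.1, delete both numerical limits from the non-target bullet. State that all remaining baseline disease is recorded as non-target, that multiple lesions in one organ may be a single entry, and that this disease counts for non-target CR and PD in Sections 11.3 and 11.4. The cost is a few words and at most one extra baseline entry per organ. No scans are added, because baseline and week-6 imaging are already scheduled in Sections 9.1 and 10.4.

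For patients already assessed, a check of stored baseline and week-6 reports for lesions beyond the caps is optional. If done, define it as a sensitivity analysis of week-6 Efficacy, ORR and PFS. Have it carried out without reference to dose, and report it beside the original result without replacing that result. It should also state how many patients had lesions beyond the caps, which is the missing figure here. The cost is a little re-coding. The drawback is that it is post hoc in an open-label trial whose results are known, hence the safeguards.

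Separately, reconcile the node-measurement wording across Sections 4.2, 8.3 and 11.1.

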 - Grade 3 tumor flare (defined as local pain, irritation or rash localized at sites of known or suspected tumor)
 - A transient (resolves within 6 hours of onset) Grade 3 infusion-related AE
 - Grade 3 hypertension that can be controlled with medical therapy
 - Any clinically meaningful Grade 3 non-hematologic laboratory value if:
 - Medical intervention (other than electrolyte repletion) is required to treat the patient, OR
 - The abnormality leads to hospitalization, OR
 - The abnormality persists for > 1 week.

Beginning on day 1 of the study, patients will each be treated with a pre-specified daily oral dose of MGCD516 determined by the Lo-EffTox method. Following 2 weeks of MGCD516 monotherapy, nivolumab will additionally be initiated at a dose of 240 mg intravenously (IV) every 2 weeks. Patients who have received at least 6 infusions of nivolumab 240 mg IV every 2 weeks with no DLTs related to nivolumab, will be allowed as an option to transition to the nivolumab schedule of 480 mg IV every 4 weeks. No other dose or schedule modifications will be allowed for nivolumab. A maximum of 60 patients will be treated in up to 20 cohorts of size 3, with the first cohort treated at the pre-specified dose of 80 mg of MGCD516 per day. All

Proprietary of MD Anderson Cancer Center

successive doses will be chosen by the Lo-EffTox method, and no untried dose level will be skipped when escalating. The Lo-EffTox design will be implemented using the specialized computer program developed by Jin et al.⁶⁰ The study biostatistician [name], [name], or [name] in the Biostatistics Department should be consulted as necessary during trial conduct. Secondary outcomes will include progression-free survival (PFS) time, overall survival (OS) time, objective response rate (ORR), and quality of life (QOL).

Patients will receive baseline staging studies with CT or MRI and be assessed for treatment response (RECIST 1.1) by CT or MRI at week 6 (+/- 7 days) as detailed on Sections 9 and 10 of the protocol.

Patients will continue to receive combination therapy of MGCD516 plus nivolumab on protocol until disease progression or unacceptable treatment-related toxicity. Patients will be allowed to continue study therapy after initial investigator-assessed RECIST 1.1-defined progression if they are deemed by the investigator to be deriving clinical benefit and tolerating study drug(s), as described in Section 8.3.

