11.6 Time -to- Event Assessment of Response

Time to Response: From the start of study drug to the first observation of a response (the first of two confirmatory measurements).

Duration of Response: From the first observation of a response (the first of the two confirmatory statements) to the first observation of progressive disease, or to death due to any cause, or early discontinuation of treatment due to progressive disease.

Time to Progression: From the start of study drug to the first evidence of progression.

Progression-free survival (PFS): Time from the start of the study drugs until disease progression (based on RECIST 1.1 criteria) or death

Survival: Survival will be calculated from the start of the study drugs to death due to any cause.

Patients in Long Term Extension Phase will not have formal RECIST measurements. The treating physician will evaluate patient for overall continued benefit.

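### Target-lesion progression is a 20% rise with no absolute minimum, so in patients with small tumour sums reading error alone can create a PFS event

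*Combined protocol and SAP*

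**What the plan says.** Section 11.2 calls target-lesion progression "At least a 20% increase in the sum of the longest diameter of target lesions, taking as reference the smallest sum longest diameter recorded"; the reference period begins when treatment starts. A new lesion also counts. Section 11.4 uses the same reference for best overall response: "taking as reference for progressive disease the smallest measurements recorded since the treatment started". Stable disease is what remains: "Insufficient shrinkage to qualify for partial response, or insufficient increase to qualify for progressive disease". Any weakness in the progression rule therefore carries into stable disease. Neither the best-overall-response table nor any other section adds a minimum absolute increase.

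Inclusion criterion 3 (Section 4.2) says "Patients must have at least one measurable site of disease", and the size limit is "10 mm with more sensitive techniques such as MRI or spiral CT scan". The smallest baseline sum that the plan admits is thus 10 mm.

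Three places name RECIST 1.1 without restating its thresholds:
- Section 5.3: patients are "assessed for treatment response (RECIST 1.1) by CT or MRI at week 6".
- Section 11.1: "Progression-free survival (PFS) and objective response rate (ORR), each based on RECIST 1.1 criteria".
- Section 11.6, on PFS: "Time from the start of the study drugs until disease progression (based on RECIST 1.1 criteria) or death".

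Section 11.1 also says simply RECIST, without a version, just before the written thresholds begin.

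**The concern.** A purely relative threshold becomes very small in millimetres when the reference sum is small, and the reference can only fall as scans accumulate. In a patient whose tumour has not changed, one low reading followed by one high reading can meet the rule.

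Three outcomes depend on it. PFS ends at the first such reading. Duration of response (Section 11.6) ends there too, and deep responders face the tightest threshold: a sum that falls from 30 mm to 12 mm is progression at 1.2 × 12 = 14.4 mm, a rise of 2.4 mm. Efficacy in the dose-finding model (Section 14.1) counts stable disease within 6 weeks as a success, so a false progression at the first scan would turn a success into a failure.

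Other provisions do not remove the problem. The irRC table in Section 11.5 has a 25% threshold and a repeat observation at least 4 weeks apart, but the week 6 assessment, ORR and PFS are tied to RECIST 1.1. Section 8.3 lets treatment continue after progression, but dates the event for analysis at the initial progression, so a later, smaller reading does not restore PFS.

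**Working it through.** The plan gives no figure of its own on this point, so there is none to reproduce.

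**Step 1: millimetres needed.** Inputs are the 20% rule (11.2) and the 10 mm entry limit (4.2). The rise needed as written is 0.20 × reference sum. With an absolute minimum m it is the larger of 0.20 × sum and m. The documents give no m; 5 mm is assumed here.

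| Reference sum (mm) | Rise needed as written (mm) | Rise needed with 5 mm minimum (mm) | A 2 mm rise as % of sum |
|---|---|---|---|
| 8 | 1.6 | 5 | 25.0 (PD) |
| 10 | 2.0 | 5 | 20.0 (PD) |
| 12 | 2.4 | 5 | 16.7 |
| 15 | 3.0 | 5 | 13.3 |
| 20 | 4.0 | 5 | 10.0 |
| 25 | 5.0 | 5 | 8.0 |
| 50 | 10.0 | 10 | 4.0 |

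A 2 mm rise is enough only at a reference sum of 10 mm or less. A 5 mm minimum alters the rule only below 5 / 0.20 = 25 mm.

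**Step 2: false progression at week 6.** Assumptions: true sum L unchanged; each reading is L plus an independent normal error with SD s; s = 1 mm, range 0.5 to 1.5. At the first scan the reference is the baseline reading. Progression needs follow-up − 1.2 × baseline ≥ 0. That difference has mean −0.2L and SD s√(1 + 1.44) = 1.562s, so

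P = 1 − Φ(0.2L / 1.562s).

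At s = 1 mm:
- L = 10: 2.0 / 1.562 = 1.28, P = 10.0%
- L = 12: 2.4 / 1.562 = 1.54, P = 6.2%
- L = 15: 3.0 / 1.562 = 1.92, P = 2.7%
- L = 20: 4.0 / 1.562 = 2.56, P = 0.5%

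This formula lets the baseline reading fall below 10 mm, but such a patient would not meet inclusion criterion 3. If the pre-study scan is also the baseline, only baseline readings of 10 mm or more count. Simulation with that condition gives the week 6 column below.

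**Step 3: accumulation over scans.** Section 10.4 schedules imaging at weeks 6 and 12 and then every 12 weeks, so the first four scans fall at weeks 6, 12, 24 and 36. Each reading is compared with the smallest earlier reading. Results are from simulation under the Step 2 assumptions, with baseline reading at least 10 mm (up to 1,000,000 patients per setting). The SD applies to the whole sum. Brackets give the range for SD 0.5 to 1.5 mm.

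| True sum (mm) | False PD at week 6, SD 1 mm | False PD on at least one of four scans, SD 1 mm (range) |
|---|---|---|
| 10 | 0.5% | 38% (3 to 63%) |
| 12 | 4.8% | 34% (1 to 62%) |
| 15 | 2.7% | 18% (0 to 50%) |
| 20 | 0.5% | 4% (0 to 27%) |

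At SD 1.5 mm the week 6 figures are 2.6% at 10 mm, about 10% at 12 and 15 mm, and 4.4% at 20 mm.

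With an added 5 mm minimum, the four-scan risk is 0.1 to 0.2% at SD 1 mm and about 5 to 7% at SD 1.5 mm across these sums.

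**Step 4: a bound on the week 6 effect.** Section 3.4 reports disease control in 37 of 42 patients, leaving 42 − 37 = 5. If disease control follows Section 11.4, where best response runs only until progression, at most 5 of 42 (11.9%) had progression at week 6, true progressors included.

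**The case against.** The best reply is that RECIST 1.1 is named for the week 6 assessment, ORR and PFS, and may itself supply a minimum that readers applied. The documents do not reproduce those criteria, so this cannot be settled from them. It does not close the gap: 11.2 writes out a rule of its own, and two readers following the protocol could classify the same scan differently. Equally, nobody can infer from these documents that the reported results were derived without a minimum.

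Several stronger readings are tempting and do not stand:
- *A tenth of small-sum patients lose week 6 Efficacy through reading error.* A reader might take the 10.0% in Step 2 that way. It depends on baseline readings below the entry limit; with that limit applied, the figure at 10 mm is 0.5% (0.0 to 2.6%).
- *Responders with a low nadir threaten the primary outcome.* At week 6 the reference is baseline. The nadir problem arises later and touches PFS, a secondary outcome, and duration of response, which 11.6 defines but Section 14.1 does not list.
- *The comparison between doses is distorted.* Section 3.4 does use PFS to separate 80 mg from 120 mg, but no difference in tumour sums by dose is given, so no distortion is shown.
- *Any small tumour is at risk from 2 mm.* That holds only at 10 mm or less. Up to five target lesions may be summed, chosen by size and suitability for repeated measurement (11.1), so a single 10 mm lesion is the extreme case.

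It is also fair to say that the 1 mm reading SD and the 5 mm minimum are assumptions, and that correlated errors from a consistent reader would lower the risks.

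**Conclusion.** The concern holds as an endpoint-definition gap. Followed as written, 11.2 allows reading error to date a false progression in patients with small reference sums, and no other section protects the RECIST-based endpoints. The main effect is on PFS and duration of response, through accumulation against a running minimum.

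At week 6 the effect on Efficacy is small at SD 1 mm, and the reported disease control leaves little room for a large one. Even at the upper end of the assumed SD, it concerns only patients with small sums.

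The size rests on the assumed SD, independent errors, an unchanged tumour over 36 weeks and a baseline reading of at least 10 mm. The distribution of tumour sums is not given, so the number of patients affected cannot be calculated and may be small.

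**What to change.** In 11.2, require for target-lesion progression a rise of at least 20% and also of at least a stated absolute minimum. Stable disease then follows. A 5 mm value is an example, not a figure from the documents; it changes nothing at reference sums of 25 mm or more. Say explicitly that this rule and the RECIST 1.1 criteria named in 5.3, 11.1 and 11.6 are the same, or which governs. Because 11.1 asks for centimetres without a precision, also state the number of decimals.

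As a sensitivity analysis, re-derive PFS, duration of response and week 6 Efficacy from the recorded diameters for patients whose reference sum was below 25 mm, and report how many there are.

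The cost is one clause and a programmed check on diameters already collected. The downside is that true growth in very small lesions may be called one scan later. The proposal concerns endpoint classification only, not decisions on stopping treatment.
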